#### 4.4 Source of Cases

At each research center, all eligible patients will serve as observation subjects for this cohort study. Patients will be assigned to respective observation cohorts based on their actual prescription status, with enrollment for each group continuing until the target number is reached.

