### 6.2 Effectiveness Observation Items

**(1) Joint swelling and pain relief rate: After the first dose, DAS 44 score was < 1.6, and decreased by more than 0.6 before and after treatment.**

Disease Activity Score of 44 Joints Based on CRP (DAS 44 -CRP): It assesses the degree of joint swelling and pain. The calculation formula is as follows:

$$\text{DAS44 - CRP} = 0.54 \times \sqrt{RAI} + 0.065 \times \sqrt{SJC44} + 0.17 \times \ln(CRP + 1) + 0.072 \times GH + 0.45$$

**44 assessed joints:** including both hand metacarpophalangeal joints (MCP1-5), proximal interphalangeal joints (PIP2-5), thumb interphalangeal joints, both wrists, both elbows, both shoulders and both knees, as shown in the figure below:

**Swollen joint count (SJC):** The number of swollen joints among 44 joints was recorded .

**CRP level:** Record laboratory test results in mg/dL (CRP).

**VAS score:** Patients mark the disease activity on a 0-100 mm visual analog scale based on their own feelings, with 0 representing no activity and 100 representing extreme activity.

2) Disease activity grading of joint swelling and pain (based on DAS 44 score):

Low activity ( DAS 44 < 1.6 )

Moderate activity ( 1.6≤DAS44 < 2.4 )

High activity ( 2.4≤DAS 44 ≤ 3.7 )

Severe activity (DAS 44 > 3.7 )

3) Evaluation of treatment response at the time of disease remission (based on reduction in DAS 4 score):

Good response (DAS 44 >1.2)

General response (0.6<DAS 44 ≤1.2)

No response (DAS 44 ≤ 0.6)

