## 10 Statistical analysis

SAS version 9.4 or above was used for data statistical analysis.

All statistical tests were two-sided, and  $P < 0.05$  was considered to be statistically significant.

The description of quantitative indicators will calculate the number of cases (N), mean (Mean), standard deviation (SD), median (Median), minimum (Min) and maximum (Max). When comparing between groups, t-test or analysis of variance was used. The description of categorical indicators uses the number of cases (N) and percentage (%) of each category. When comparing between groups, chi-square test or Fisher's exact probability method was used. The Kaplan-Meier (KM) test was used to estimate the survival function and calculate the median time for time-to-event variables. The survival curves between different groups were compared based on the Log-Rank test, and the corresponding P value was calculated.

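### If the ordered DAS44 activity and response grades are compared between cohorts, section 10 offers only chi-square/Fisher, which is valid but ignores their order

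*Protocol*

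**What the plan says.** Protocol section 6.2(1), among the effectiveness items, has three layers for joint swelling and pain.

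- The named outcome is a relief rate, a yes/no criterion: "DAS 44 score was < 1.6, and decreased by more than 0.6 before and after treatment".
- Sub-item 2 is a four-level scale (low, moderate, high, severe) cut from the score: "Disease activity grading of joint swelling and pain (based on DAS 44 score").
- Sub-item 3 is a three-level scale (good, general, none) cut from the fall in the score: "Evaluation of treatment response at the time of disease remission".

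Protocol section 10 sorts outcomes into quantitative, categorical and time-to-event.

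- Quantitative: "When comparing between groups, t-test or analysis of variance was used".
- Categorical: "The description of categorical indicators uses the number of cases (N) and percentage (%) of each category", followed by "When comparing between groups, chi-square test or Fisher's exact probability method was used".
- All types: "All statistical tests were two-sided", at the 0.05 level.

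Ordered and unordered categories are not separated, and no rank, trend or ordinal-regression method is named. There are three cohorts, formed by treatment received: "Patients will be assigned to respective observation cohorts based on their actual prescription status" (section 4.4). Section 3.1 takes all patients who can be collected and gives no number. Section 4.4 mentions a target per group without stating it.

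**The concern.** Pearson chi-square and Fisher's exact test give the same P value if the grade labels are shuffled. The clinical question about a graded scale is usually whether one cohort sits lower or higher on it. An order-blind test spreads its power over every possible pattern of difference, so it uses 2 or 3 degrees of freedom for two cohorts and 4 or 6 for three. A rank test needs 1 or 2.

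A real shift towards milder grades could therefore be missed more often than necessary. A significant result could also reflect a pattern in which neither cohort is better overall. The enrolled number is whatever the outbreak yields, so the study cannot rely on its size to make up for an inefficient test.

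**Working it through.** **No figure to reproduce.** The protocol states no power, effect size, sample size or grade distribution. Everything below except the level, the number of grades and the number of cohorts is an assumption.

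**Inputs from the protocol.** Two-sided alpha 0.05 (section 10); 4 and 3 ordered levels (section 6.2(1)); three cohorts (section 5.1), compared either as two at a time or all together.

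**Degrees of freedom.** Chi-square: (cohorts − 1) × (levels − 1). Rank test: cohorts − 1.

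- Two cohorts: 1 × 2 = 2 (response) or 1 × 3 = 3 (activity), against 1.
- Three cohorts: 2 × 2 = 4 or 2 × 3 = 6, against 2.

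**Step 1: approximation.** Under a proportional-odds shift, nearly all of the departure from the null lies in the direction that the rank test looks at. Both statistics then have about the same noncentrality λ, and power is P(χ²(df, λ) > critical value). The 5% critical values are 3.841, 5.991, 7.815, 9.488 and 12.592 for 1, 2, 3, 4 and 6 df.

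At 80% rank-test power:

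- Two cohorts: λ = 7.849. Chi-square power is 70.9% on 2 df and 64.5% on 3 df, a loss of 9.1 and 15.5 points.
- Three cohorts: λ = 9.635. Chi-square power is 69.8% on 4 df and 62.5% on 6 df, a loss of 10.2 and 17.5 points.

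Points lost by chi-square at other levels of rank-test power:

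| Rank-test power | 3 levels, 2 cohorts | 3 levels, 3 cohorts | 4 levels, 2 cohorts | 4 levels, 3 cohorts |
|---|---|---|---|---|
| 30% | 6.9 | 7.3 | 10.3 | 10.8 |
| 50% | 9.9 | 10.7 | 15.5 | 16.7 |
| 70% | 10.3 | 11.4 | 16.9 | 18.8 |
| 80% | 9.1 | 10.2 | 15.5 | 17.5 |
| 90% | 6.5 | 7.4 | 11.6 | 13.5 |

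This gives about 7 to 11 points for the response grade and 10 to 19 for the activity grade.

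**Step 2: simulation.** Tables were simulated (8,000 per scenario) for four assumed baseline distributions per scale, odds ratios from 1.3 to 2.5, and 50 to 300 patients per cohort in two or three equal cohorts. Over all scenarios the loss ran from 0 to 12 points (3 levels) and from 0 to 20 points (4 levels). It was about 1 to 11 points where rank-test power was below 30%, and 0 to 7 where it was above 95%.

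**Step 3: validity.** With no true difference, chi-square rejected in 4.7% to 5.0% of tables, so its level is correct.

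**Step 4: a case that goes the other way.** Take 25/25/25/25% against 35/15/15/35%, with 100 per cohort. The pooled expected counts are 30, 20, 20 and 30, and every cell departs by 5. So λ = 2 × (25/30 + 25/20 + 25/20 + 25/30) = 8.33 on 3 df. Simulated power is 68% for chi-square. Mean ranks are equal by symmetry, and the rank test rejects in 5.5% of tables, which is about its null rate.

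**The case against.** Several arguments on the other side are sound.

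- **The comparison is an inference.** Nothing says the grades will be tested between cohorts, and they may serve only as descriptive scales. This stands, so the point is conditional.
- **The main joint outcomes are untouched.** The relief rate is binary, so chi-square/Fisher suits it. The undivided DAS44 score has its own t-test/ANOVA route, which can pick up a shift. This stands and limits the point to a supporting scale.
- **It belongs in the SAP.** A SAP not shown here may name an ordinal method. However, section 10 does not leave the matter open: it states a test for categorical indicators without exception, and a rank test for the grades would depart from it. The multivariate methods in section 9.1.4 leave room for a proportional-odds model but do not assign one to the grades.
- **A rank test is not uniformly better.** Step 4 shows this. A split towards both extremes is conceivable in unrandomised cohorts on individually tailored treatment, and a rank test would almost always miss it. This stands.
- **Direction.** The required N and percentage per grade already show it, and a three-cohort Kruskal-Wallis P value does not. This also stands. It is why an effect estimate is needed beside the rank test.

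A reader might infer that the plan forfeits 7 to 19 points of power as a matter of fact, or that its test is wrong. The documents support neither. They contain none of the inputs to the power figure, and the test holds its level.

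**Conclusion.** The point holds as a conditional loss of efficiency. If the DAS44 grades are compared between cohorts, the only section 10 rule that fits them ignores their order. Under an assumed proportional-odds shift, equal cohorts and a rank test with about 30% to 90% power, the cost is about 7 to 11 points for the three-level response grade and 10 to 19 for the four-level activity grade. Over all scenarios examined it ranges from 0 to about 20 points. For non-monotone differences chi-square can be the stronger test. A naturally ordered scale and an effectiveness question make a consistent shift the more relevant alternative, so an ordinal method is the better default. No conclusion about the relief rate, the DAS44 score or type I error follows.

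**What to change.** In section 10:

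1. Limit chi-square/Fisher to unordered or two-level indicators.
2. State that ordered grades, if compared, are tested by Wilcoxon rank-sum for two cohorts or Kruskal-Wallis for three.
3. For each pair of cohorts, report the common odds ratio from a proportional-odds model with its 95% CI, adjusted as section 9.1.4 foresees. Report it in every case, because this is what shows direction and because the cohorts are not randomised.
4. Keep the N and percentage per grade that section 10 already requires.

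The cost is a sentence or two. No new data are needed, and the methods are standard in the SAS software that section 10 names. The small downside is that the rank test can miss a non-monotone pattern. Item 4 keeps such a pattern visible.

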## **11 Ethical requirements**

Since this study is an observational study, it does not interfere with normal clinical medical services, nor does it interfere with patients' medical treatment and medication behavior. Therefore, in addition to passing the ethics review at the clinical lead unit, other research centers can conduct ethics filing as needed, or conduct ethics review of this project, but the focus of the review should be the feasibility of this project in the center. After the review and approval, if major modifications to the trial protocol are required, it should be submitted to the ethics committee of the clinical lead unit for review and approval again.

Only researchers and monitors involved in clinical research may have access to the personal medical records of the research subjects, and they will include confidentiality in the signed researcher statement or confidentiality commitment. The ethics committee and the drug supervision and administration department have the right to review the clinical research records. When processing data, the data will be anonymous, omitting information that can identify the individual identity of the research subjects. The medical records of the research subjects are kept in the data archives of the drug clinical research institution with strict security and confidentiality measures.

## **12 Data Retention**

All paper and electronic materials (investigator's manual, research plan, case observation form, monitoring and audit record report, etc.) of this study will be kept by Guangdong Provincial Hospital of Chinese Medicine. All materials will be kept for at least 5 years after the termination of the study.
